5.1. Recruitment

The study will be carried out in adults in areas endemic for *S. stercoralis* in Kampong Chhnang province, Cambodia.

The adult community members will be invited to participate in an open community information meeting to explain the purpose and procedures of the study, including potential benefits and risks. Potential participants will be encouraged to ask questions in an open discussion followed by this meeting.

Those adults interested in the study will be invited to complete the process of informed consent. See section 9.3 for details on obtaining informed consent. Only those participants who have written informed consent will be assessed for study eligibility criteria during screening procedures.

5.2. Inclusion criteria

1. Males and females aged 18-65 years infected with *S. stercoralis* (positive in at least one of the three provided stool samples or at least two of the sextuplicate Baermann assays (0.07 LPG in 10 g of stool)).
2. Written informed consent signed by the participant him/herself. In case the person is illiterate, an impartial witness that can read and write has to sign the consent and the illiterate participant has to give a thumbprint.
3. Agree to comply with the study procedures, including to be examined by a study physician before treatment and to provide three stool samples at the beginning (baseline) and three stool samples approximately two to three weeks after receiving treatment (follow-up 1). Further three stool samples are asked for at each long-term follow-up scheduled at 42-49 and 63-70 days-post-treatment.

5.3. Exclusion criteria

- Presence of acute or uncontrolled systemic illnesses (e.g. severe anemia, fever) as assessed by a medical doctor, upon initial clinical assessment.
- History of severe chronic disease or major systemic illnesses, e.g. severe anemia, severe chronic heart, liver or renal disease as asked by the medical doctor, upon initial clinical assessment.
- Treatment with anthelmintics (e.g. diethylcarbamazine [DEC], suramin, ivermectin, mebendazole or albendazole) within 4 weeks before study start.

- Attending other clinical trials during the study period.
- Pregnancy, lactating, and/or planning to become pregnant within the study period.
- Known allergy to study medications (i.e. moxidectin or ivermectin).
- Use of medication with known interaction on the study drug.

Participants who were diagnosed with a STH infection, but who were excluded from the study due to one or several of the above-mentioned exclusion criteria, including withdrawals, will be offered standard anthelminthic treatment (i.e. ivermectin at a single dose of 200 µg/kg).

5.4. Criteria for discontinuation of trial

A participant can be discontinued from the study for the following reasons:

1. withdraws from the study.
2. at the discretion of the PI or co-PI, if the participant is not compliant to the requirements of the protocol.

Discontinued participants will not be replaced. If, for any reason, a participant is discontinued from the study before the end of treatment evaluations, the planned procedures (AEs monitoring) will be conducted. Data obtained prior to the participant's withdrawal will be included in analysis. Data of withdrawn participants are fully anonymized once analysis is completed.

5.5. Treatment of participants

2 mg tablets of moxidectin and moxidectin placebo tablets will be obtained from Medicines Development for Global Health (MDGH), Australia. Ivermectin (3 mg) will be purchased from Merck, Switzerland and matching ivermectin placebo tablets will be produced and a certificate of manufacture and analysis provided by the University of Basel. The body weight of each participant will be recorded to calculate and administer the correct dose of ivermectin (200 µg/kg). 8 mg (4 pills of moxidectin or moxidectin placebo) and the appropriate doses of weight-dependent ivermectin or its placebo will be calculated and administered to all participants. Each person (i.e. moxidectin 8 mg and ivermectin 200 µg/kg) will receive the maximum number of ivermectin tablets with regard to their weight category or the corresponding number of placebo tablets, and the four 2 mg moxidectin tablets or equal number of placebo tablets. The tablets will be handed out from the drug container according to the randomization list. The person conducting the recruitment and defining the order in which patients receive treatment will be masked to the randomization sequence so to warrant allocation concealment.

All drugs will be administered in the presence of the PI or co-PI and the physician, and ingestion confirmed. This will be recorded with the time and date of dosing. The tablets will as long as applicable be stored in the original package and at any time (except treatment day) be stored according to manufacture prescription, sealed and away from light. The PI or co-PI is responsible for drug accountability at the study site. Maintaining drug accountability includes careful and systematic study drug storage, handling, dispensing and documentation of administration.

After ingestion of the medication at every administration time point, the participants will be observed for 3 hours to ensure retention of the drug. Vomiting within 1 hour post-dosing will require re-dosing. The participants will not be allowed more than one repeated dose. No re-administration will be needed for participants vomiting after one hour. In case any SUSAR will be observed, any further treatment will be put on hold until the data has been reviewed and a decision taken within the entire study team whether the study can be continued or has to be stopped. On the treatment day, participants presenting a serious medical situation, as judged by the physician, will be kept at the hospital level under close supervision by a medical team. Also, in order to not break the surveillance of the undesirable effects of those whom we will allow to go back home at the end of the treatment day, security measures will be taken: (i) a card containing at least three phone numbers of the investigators and the study physician will be given to the participant him/herself. Participants will further be asked not to take any drugs other than those prescribed by the study medical team.

Treatment will be done community-based in local community buildings. Infrastructure as required for the study needs (i.e. tables, chairs, a cover from rain and sun) will be installed as necessary at the specific study days. Participants will receive a local breakfast two hours prior to treatment as well as lunch and snacks during the day once absorption of the drug is complete.

5.6. Concomitant therapy

All medications taken one month before and during the study period must until the last stool examination at day 63-70 (follow-up) be recorded with indication, dose regimen, date and time of administration.

Medication(s)/treatment(s) permitted during the trial

- Analgesics and antipyretics are allowed to be given to the participants in case of fever, antiemetics to prevent nausea and vomiting and/or antibiotics to prevent or treat bacterial superinfection.

Medication(s)/treatment(s) NOT permitted during the trial

- No other active drugs against helminths are permitted during the trial. Participants receiving active antihelminthic concomitant medication during the trial will not be discontinued; however a case-specific assessment will be done at the time of data-analysis.

6. Assessment of safety

6.1. Adverse event definition

Few adverse events have been reported following moxidectin or ivermectin administration in STH-infected individuals. The most common AEs were abdominal cramps, headache, nausea, diarrhea, fever and vertigo [11, 12, 45, 46].

6.1.1. Types of adverse events

The term “adverse event” is defined as:

Any untoward medical occurrence in participants or clinical investigation subject administered a pharmaceutical product and which does not necessarily have to have a causal relationship with this treatment.

An AE can therefore include any of the following events, which develop or increase in severity during the course of the study, after administration of the study product:

- a) Any unfavorable and unintended sign (including an abnormal laboratory finding, for example), symptom, or disease temporally associated with the use of a medicinal product, whether or not considered related to the medicinal product.
- b) Any abnormality detected during physical examination.

These data will be recorded on the appropriate CRF sections, regardless of whether they are thought to be associated with the study or the drug under investigation. “Associated with the drug” means that there is a reasonable possibility that the event may have been caused by the drug.

6.1.2. Severity grading

Adverse signs or symptoms will be graded by the investigator as mild, moderate, severe or life threatening according to the following definitions:

(https://evs.nci.nih.gov/ftp1/CTCAE/CTCAE_4.03_2010-06-14_QuickReference_5x7.pdf).

Grade Definition

1. Mild: the participant is aware of the event or symptom, but the event or symptom is easily tolerated.
2. Moderate: the participant experiences sufficient discomfort to interfere with or reduce his or her usual level of activity.
3. Severe: significant impairment of functioning: the participant is unable to carry out his or her usual activities.
4. Life threatening or disabling.
5. Death related to adverse events.

6.1.3. Relatedness

Relatedness will be assessed as defined below based on the temporal relationship between the AE and the treatment, known side effects of treatment, medical history, concomitant medication, course of the underlying disease and trial procedures.

Possibly related: an AE which can medically (pharmacologically/clinically) be attributed to the study treatment.

Unrelated: an adverse even which is not reasonably related to the study treatment. A reasonable alternative explanation must be available.

An AE that is determined to be related to the administration of a study product is referred to as an “adverse drug reaction”.

6.1.4. Types of adverse events

Expected adverse event: Any adverse event possibly related to the study drug administration reported in the literature and/or on the drug package leaflets for moxidectin and/or ivermectin.

Unexpected adverse event: Any adverse event possibly related to the study drug administration, the nature, frequency specificity or severity of which is unanticipated and not consistent with the available risk information described for these drugs.

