In this trial, we will test for non-inferiority of the recommended 8 mg of moxidectin against the standard dose of 200 µg/kg ivermectin.

Moreover, there is a need to explore whether the longer half-life of moxidectin ($T_{1/2}$: 491-832 h) compared to ivermectin ($T_{1/2}$: 16-32 h) could reveal a benefit in the treatment of *S. stercoralis* infections [13, 22]. Potential extended effects will be examined through a prolonged efficacy, safety and tolerability assessment scheme. Thus, additional follow-ups (besides the standard 14-21 days) will be conducted, namely 42-49 days post-treatment in correlation to the duration

of an autoinfection cycle and 63-70 days post-treatment analogous to a second auto-infection cycle as well as the elimination time of moxidectin from blood [13, 23].

Besides the study will be complemented by displaying larval excretion pattern over the whole time course after treatment until 28 days post-treatment and guide more appropriate follow-up periods. The appropriate follow-up time points are today not evaluated for infections with *S. stercoralis*.

Last, strongyloidiasis cannot solely be fought with chemotherapy, yet there is a need for multifaceted approaches including environmental and behavioral adaptation to attain disease control and elimination [30]. This study will be complemented by assessing socioeconomic characteristics, access to sanitation and water facilities as well as hygiene to identify influencing factors with regard to infection intensity and reinfection [30, 31].

Ultimately, results from this trial will inform decision on how moxidectin could be used to treat strongyloidiasis on a patient level and evidence will be strengthened to include moxidectin in the drug armamentarium for future community-wide chemotherapy.

3. Trial objective and purpose

The primary study objectives are

To determine if the efficacy in terms of cure rate of an oral 8 mg of moxidectin is non-inferior to the standard dose of a single oral ivermectin application (200 µg/kg), in 350 *S. stercoralis*-infected adults in Cambodia.

The secondary study objectives are

- 1.) to determine safety and tolerability of an oral moxidectin dose in 175 adults infected with *S. stercoralis*.
- 2.) to compare the efficacy based on larvae reduction rates of the different treatments drugs and regimens in 350 adults infected with *S. stercoralis*.
- 3.) to evaluate the CRs of the different treatments against STH co-infections.

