4.4. Measure to minimize bias

Study participants eligible for treatment will be randomly assigned to one of the two treatment arms using a computer-generated stratified block randomization code. The random allocation sequence with varying random blocks of 4 and 6 will be provided by a statistician not involved in enrolment, treatment, and data collection. Separate sequences will be generated for three levels of baseline infection intensity (light ≤1 LPG, moderate >1-10 LPG and heavy >10 LPG). The codes will be held at the Swiss Tropical and Public Health Institute. A copy of this code will be kept in a sealed envelope by one of the co-investigators and will only be opened in emergency situations, determined by the principal investigator (PI) upon consultation with the co-investigators (co-PI). Allocation concealment will be maintained by masking the randomization sequence from the team member conducting the recruitment. Participants are blinded towards the study drugs (double-blinded).

Masking of the outcome assessor is ascertained in all treatment arms since the laboratory technicians determining the larvae counts and presence of egg for efficacy assessment will

have no knowledge of the participants assignment to treatment arm. The blinding will be maintained throughout the trial until data entry and processing are complete and the data have been verified. Following release of the final data, the randomization codes will be released.

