6.1.6. Suspected unexpected serious adverse reactions

A suspected unexpected serious adverse reaction (SUSAR) is an unexpected adverse drug reaction which also meets the definition of serious adverse events.

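### Minor wording fix: Section 6.1.4 judges expectedness against both drugs pooled, so a serious moxidectin reaction known only for ivermectin would not trigger the mandatory treatment hold

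*Combined protocol and SAP*

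**What the plan says.** Section 6.1.4 sets two definitions. A possibly related event is expected if it is "reported in the literature and/or on the drug package leaflets for moxidectin and/or ivermectin". It is unexpected if it is one the nature, "frequency specificity or severity of which is unanticipated and not consistent with the available risk information described for these drugs". Both draw on the two drugs together, and neither names the product that the participant took.

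Section 6.1.6 builds on this: "A suspected unexpected serious adverse reaction (SUSAR) is an unexpected adverse drug reaction which also meets the definition of serious adverse events". Section 5.5 then attaches an action to the label: "In case any SUSAR will be observed, any further treatment will be put on hold until the data has been reviewed". The whole study team decides whether the trial continues.

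On masking, Section 4.4 describes a double-blind trial. The randomization codes are held at the sponsor institute. A sealed copy is kept by a co-investigator for emergencies, and the PI decides, after consulting the co-investigators, what counts as one. Section 4.4 does not mention classification of safety events.

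**The concern.** In a two-drug trial, an event is new information when it is not already known for the drug that the participant took. Pooling lets the comparator's safety record make a reaction expected for the investigational product. The first secondary objective in Section 3 is "to determine safety and tolerability of an oral moxidectin dose in 175 adults", so a serious moxidectin reaction so far seen only with ivermectin is one that the trial should want to review before dosing more people.

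The plan does not treat the drugs as interchangeable. Section 2 claims a lower neurotoxic potential for moxidectin and gives half-lives of 491-832 h, against 16-32 h for ivermectin. A reaction known for one drug need not run the same course with the other.

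What is at stake is the automatic pause for review before further treatment.

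**Working it through.** The plan attaches no figure to this point, so the check is a trace of the definitions.

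**Step 1: from event to hold.** Section 6.1.4 decides expected or unexpected. Section 6.1.6 makes a SUSAR of a reaction that is both unexpected and serious. Section 5.5 stops further treatment on a SUSAR. A reaction that is expected at the first step cannot reach the third.

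**Step 2: which reactions change class.** Take a serious, possibly related reaction that matches the documented profile in nature, frequency, specificity and severity.

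| Row | Documented for | Product received | 6.1.4 as worded | Judged by product received |
|---|---|---|---|---|
| 1 | both drugs | either | expected, no hold | expected, no hold |
| 2 | ivermectin only | moxidectin | expected, no hold | unexpected, hold |
| 3 | ivermectin only | ivermectin | expected, no hold | expected, no hold |
| 4 | moxidectin only | ivermectin | expected, no hold | unexpected, hold |
| 5 | moxidectin only | moxidectin | expected, no hold | expected, no hold |
| 6 | neither drug | either | unexpected, hold | unexpected, hold |

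The two columns differ only in rows 2 and 4. Row 2 concerns the product under test. If the reaction departs from the documented profile, for example by being more severe or more frequent, the second definition in 6.1.4 can still make it unexpected, and the hold applies.

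**Step 3: is there another mandatory hold?** The Synopsis plans no interim analysis. Section 5.4, despite its title, deals with discontinuing individual participants. Section 11.2 sets up no DSMB. Section 9.3 permits protective action but does not require it. The SUSAR hold is therefore the only mandatory one.

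**Step 4: what does not depend on expectedness?** Section 6.3 sends every SAE to the PI within 24 hours, with a written narrative in the next 48. It also covers unanticipated problems that pose a risk. Section 6.4 sets the same deadlines for SAEs and SUSARs: 24 hours if fatal or life-threatening, otherwise at most 14 days. Section 9.1 allows an immediate change to remove a hazard, and Section 11.2 keeps advisors informed. None of this changes in rows 2 and 4.

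**Step 5: do the documents show a row 2 reaction?** They do not. Section 6.1 says "Few adverse events have been reported following moxidectin or ivermectin administration" in people with these infections and gives one list of common events for both drugs. No serious reaction is named as known for ivermectin but not for moxidectin.

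**The case against.** **The wording can be read drug by drug.** Both definitions speak of the study drug in the singular, and Section 6.1.3 ties an adverse drug reaction to a study product. The phrase naming both drugs could simply list where to look for whichever product applies. That reading is possible, but the text does not state it, and the plan gives no rule for applying it to a masked case. Section 4.4 does not forbid opening the code for a serious reaction, since the PI judges what is an emergency. It does not provide for it either.

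**Pooling suits a blinded, double-dummy trial.** It lets masked staff classify events without the code. This is a fair practical reason, although the plan does not give it. A masked rule can protect participants equally well in the other direction, by requiring that the event be known for both products before it counts as expected.

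**No affected event has been shown, and the safety net is strong.** This stands in full, and it is why the point is minor. The reaction must be serious, possibly related, absent from all moxidectin literature and leaflets, and within ivermectin's known profile. It must also occur while others are still to be dosed: treatment is a single dose, so a hold protects only participants not yet treated.

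**Stronger readings that the documents do not support.** A reader might infer that serious moxidectin reactions could go unreported. Sections 6.3 and 6.4 rule this out. A reader might infer that the team could not stop dosing. Section 9.3 lets the investigator take protective steps whether or not the protocol names them. A reader might infer that any moxidectin reaction resembling an ivermectin reaction passes as expected. The second definition in 6.1.4 still catches departures in nature, frequency, specificity or severity.

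**Conclusion.** The point holds as a minor, cheap improvement. On its plain wording, Section 6.1.4 can classify a serious, possibly related moxidectin reaction as expected on the strength of ivermectin's record alone. The trial's only mandatory hold then does not operate. What is lost is the automatic pause. Detection, SAE reporting and the power to act are intact.

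The conclusion rests on two conditions: that the definitions are applied as written and not drug by drug, and that the reaction fits ivermectin's documented profile. Its frequency cannot be sized. The documents give no risk for such a reaction and do not show that one exists, so any probability for the 175 moxidectin recipients would only restate an assumed risk. A reader might also infer that the trial needs an unblinded safety assessor or a code check for each case. It does not, because a rule that works under masking closes the gap, and a code check could disclose an allocation to the team.

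**What to change.** Add to Section 6.1.4 wording such as: *Expectedness is judged against the risk information for the product the participant received. While the case is masked, a serious, possibly related event is treated as unexpected unless it is listed for both moxidectin and ivermectin.*

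Under masking, rows 2 to 5 of the table then lead to a hold, and rows 1 and 6 are unchanged. The holds in rows 3 and 5 are the price: an occasional short pause for a reaction already known for the drug that was in fact given. No code is opened and no role is added. Sections 4.4, 5.5, 6.1.6, 6.3 and 6.4 can stay as they are.

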6.1.5. Serious adverse events

According to the ICH “Clinical Safety Data Management: Definitions and standards for expedited Reporting E2A”

(https://www.ich.org/fileadmin/Public_Web_Site/ICH_Products/Guidelines/Efficacy/E2A/Step4/E2A_Guideline.pdf) a serious SAE includes any event (experience) or reaction in any untoward medical occurrence that at any dose:

1. is fatal, results in death;

2. is life threatening, meaning, the participant was, in the view of the investigator, at immediate risk of death from the reaction as it occurred, i.e., it does not include a reaction that, had it occurred in a more serious form, might have caused death;
3. is a persistent or significant disability or incapacity, i.e., the event causes a substantial disruption of a person's ability to conduct normal life functions;
4. requires, or prolongs in-patient hospitalization;
5. is a congenital anomaly or birth defect;
6. is an important medical event, based upon appropriate medical judgment, that may jeopardize the patient or participant or may require medical or surgical intervention to prevent one of the other outcomes defining serious.

A “severe” AE does not necessarily meet the criteria for a “serious” AE. Serious adverse events are reported from the first dose of study medication to 21 days post-treatment.

SAEs that are still ongoing at the end of the study period will be followed up to determine the final outcome. Any SAE that occurs after the study period and is considered to be possibly related (definitions will be used according to the WHO-UMC system; see: <http://who-umc.org/Graphics/24734.pdf>) to the study treatment or study participation will be recorded and reported immediately.

